# **Optimal Target of Activated Clotting Time During Percutaneous Coronary Intervention and Outcomes: The Randomized OPTIMAL-ACT Trial**

The **objective of this proposal** is to identify the optimal range of the activated clotting time (ACT) during percutaneous coronary intervention (PCI) that is associated with the lowest rates of adverse clinical events. The optimal ACT target during PCI has not previously been investigated in a prospective clinical trial, leaving uncertainty regarding the level of anticoagulation intensity during coronary revascularization procedures. The **primary research hypothesis** is that in the modern cardiac catheterization laboratory, where PCI procedural duration is relatively short and rates of intracoronary stenting and dual antiplatelet therapy use is high, lower ACT targets, as compared with higher ACT targets, will be associated with lower rates of bleeding while having similar rates of ischemic events.

## **Co-Investigators:**

[name]

[name]

[name]

[name], MS

[name], MS

[name], RCIS

[name], RCIS, RCES

[name], PhD

[name]

[name]

[name]

**Rationale:** For the past three decades, unfractionated heparin (UFH) has remained the mainstay of anticoagulation during invasive cardiac procedures(1-3) and has been the only available anticoagulant in interventional cardiology for many years (4). Advantages to UFH are related to availability, familiarity, low cost, point-of-care (POC) testing using the activated clotting time (ACT), and reversibility with protamine sulfate. Use of peri-procedural anticoagulation with UFH during percutaneous coronary intervention (PCI) is recommended to reduce thrombus formation on interventional devices and thrombotic complications during PCI(4-6). POC testing allows targeting ACT values to recommended ranges, gives fairly reproducible results, and ACT values increase linearly with UFH supplementation and decrease without additional UFH over time(7). However, despite guideline suggested use of ACT monitoring in UFH-treated patients undergoing PCI, there are limited and often conflicting data regarding the association of ACT target values and outcomes(6,8-10). Importantly, data for the relationship between ACT and outcomes are sparse in contemporary PCI practice that now includes the use of lower profile equipment, high rates of intracoronary stenting, transradial procedures, and dual antiplatelet therapy(10). Early small studies found low rates of ischemic complications with low and fixed dose heparin(11,12), while pooled data from clinical trial participants suggested lower ischemic event rates with higher ACT targets of 350 to 375 seconds, though at a cost of higher rates of bleeding(8). Other studies analyzing low risk patients from clinical trials have not observed an association between ACT levels and ischemic endpoints(9,10). Despite widespread use of ACT monitoring during PCI, uncertainty remains regarding the association between ACT cutoffs and outcomes in contemporary practice, largely related to lack of randomized trials evaluating the optimum ACT target and its relation with events. Practice guidelines conclude that despite the use of recommended ACT levels, often based on empiricism and ranges used in clinical trials of PCI, the utility of ACT in clinical practice remains uncertain (4).

The pQint-of-care PracTice to IMProve use of AnticoaguLation (OPTIMAL)-ACT trial is a prospective, randomized, investigator-initiated, trial to determine the optimal ACT target value in patients undergoing PCI. This will be the first prospective outcomes trial powered to identify the optimal ACT target range for reducing the rate of in-hospital bleeding (Bleeding Academic Research Consortium and EASY grading defined (Appendix I)). Different bleeding definitions will be used to account for shift in access site practice from femoral to radial, both here at Mayo Clinic Florida, and in the United States. In addition, the EASY grading scale is unique to transradial catheterization and complications related to bleeding may be more frequent among women (13). Rates of net adverse cardiovascular events (NACE) (defined as all-cause mortality, myocardial infarction (MI), stroke, or bleeding) would be identified as a primary safety endpoint in the trial. We aim to test the hypothesis that lower ACT target values, as compared to higher ACT target values, are associated with lower risk of bleeding without compromising efficacy as assessed by the primary safety endpoint. This finding would have significant implications for improving the safety of PCI by reducing bleeding complications.

**A. Significance:** The significance of the study proposal can be highlighted by 1) the recognition of the burden of coronary artery disease (CAD), 2) the widespread adoption and performance of PCI, and 3) the limited data regarding appropriate anticoagulation intensity during PCI. CAD causes 1 out of 6 deaths in the United States. Annually, over 600,000 patients suffer a coronary event, defined as a first hospitalized myocardial infarction or CAD-related death (14). Improvements in adherence to guideline-recommended therapies for patients with ischemic heart disease, including use of coronary revascularization procedures, have impacted the decline in deaths related to cardiovascular disease over the past several years. PCI is performed commonly in the United States with an estimated 490,000 procedures in 2010 alone (15). In patients with acute coronary syndromes, early revascularization with PCI has been

demonstrated to improve outcomes. As the technical success rates of PCI have continued to remain very high, there has been a renewed interest in delivering PCI safely and reducing complications. This evolution in contemporary PCI includes use of lower profile devices, smaller caliber intravascular sheaths, shorter procedural durations, and greater adoption of transradial catheterization. In addition, strategies to mitigate bleeding have garnered greater attention given the association of bleeding with adverse short and long-term outcomes. A fundamental aspect of current PCI practice involves the use of anticoagulants during the procedure to reduce the risk of thrombus formation on interventional devices (i.e., guiding catheters, wires) and reduce the risk of abrupt vessel closure. The intensity of anticoagulation to reduce thrombotic risk is, however, on balance with increased bleeding risk, which have led to recommendations on appropriate ACT targets during PCI (4). Despite these recommended ACT targets, bleeding events are observed in 1 out of 10 patients at currently recommended ACT target ranges (8). In addition, due to the limited evidence base, guidelines have also acknowledged that “the utility of measured ACT levels in current practice should be considered uncertain”(4). Despite the influential role of an ACT value on an operator’s decision to intensify or reduce the level of anticoagulation in the patient, and thus directly impact the ischemic vs. bleeding risk-calculus, optimizing the dose of UFH during PCI has clinical equipoise. The current gaps in knowledge, therefore, underscores the need for a rigorous study of anticoagulation intensity during PCI to improve patient safety and advance scientific understanding of ACT monitoring. This has significant public health implications and tremendous potential to impact the current practice of PCI. In alignment with Mayo Clinic’s commitment to improving the safety of patient care, the knowledge gap with regard to intensity of heparinization during PCI remains an important and unanswered question in interventional cardiology.

**B. Specific Aims:** Anticoagulation is routinely administered prior to performing PCI in interventional cardiology practice and intensity of anticoagulation is monitored using POC testing for the ACT. However, current target values were derived from older, case-control studies (6,16), and supported by post-hoc retrospective analysis from trials of antithrombotic therapies (9,10). In the modern era of high rates of dual antiplatelet therapy use, low profile devices, greater attention to access site management, and shorter procedural duration, the optimal ACT target for PCI remains unknown. The overall objective of this proposal is to identify the optimal range of the activated clotting time (ACT) during percutaneous coronary intervention (PCI) that is associated with the lowest rates of adverse clinical events. The optimal ACT target during PCI has not previously been investigated in a prospective clinical trial, leaving uncertainty regarding the level of anticoagulation intensity during coronary revascularization procedures. We hypothesize that in the modern cardiac catheterization laboratory, where PCI procedural duration is relatively short and rates of intracoronary stenting and dual antiplatelet therapy use is high, lower ACT targets, as compared with higher ACT targets, will be associated with lower rates of bleeding while having similar rates of ischemic events. The specific aims of this study are as follows:

**B.1.1 Aim 1 (Primary):** The primary aim of this study of patients undergoing PCI is to compare the risk of bleeding in patients randomized to a low ACT target to those randomized to either a medium or high ACT target. We hypothesize that the risk of bleeding will be lower in those with a low ACT target compared to those with a medium ACT target as well as those with a high ACT target. See Figure 1 for ACT target ranges.

**B.1.2 Aim 2 (Primary):** We aim to estimate the incidence of both our primary study outcome (bleeding) and our primary safety endpoint (NACE) separately for those with a low, medium, and high ACT target.

**B.1.3 Aim 3 (Primary):** We aim to establish whether there is evidence of non-inferiority of a low ACT target compared to a high ACT target with respect to the proportion of patients undergoing

PCI with respect to NACE. We hypothesize that the rate of NACE is the same as or lower than that for patients with a high ACT target.

B.1.4 Aim 4 (Secondary): We aim to study the impact of sex, access-site (i.e., radial vs femoral), and concomitant use of glycoprotein (GP) IIb/IIIa inhibitors on the association of ACT target with bleeding. It has been shown that female sex is associated with higher ACT targets during PCI (17), and work from our group has shown an important observed interaction with myocardial infarction risk in women, but not men, with ACT targets >350 seconds(18). This observation of a potential differential sex-specific interaction has not previously been reported and requires validation in a prospective study. In addition, it has previously been shown that women appear to be at higher risk for developing forearm bleeding complications after transradial catheterization. The use of transradial PCI has steadily increased in the United States, though adoption of this technique remains lower than that observed in Canada and Europe. However, recent internal PCI data from the cardiac catheterization laboratory at Mayo Clinic Rochester has shown increasing utilization of the radial artery for PCI, now over 50%. At Mayo Clinic Florida, the percentage of radial access is over 70% and is considered the default access site for catheterization. It remains unknown whether ACT targets can be similarly interpreted for radial PCI, as these original targets were derived from studies in primarily transfemoral access cohorts with larger vascular access sheaths. Finally, the additional use of GP IIb/IIIa inhibitors in UFH-treated patients has been associated with higher rates of major and minor bleeding (9), thus lower ACT target values (i.e., 200-250 sec) are recommended in patients concomitantly treated with these agents. In the Mayo Clinic experience, there was no apparent interaction by GP IIb/IIIa inhibitor status when testing the association of ACT values to outcomes, however, baseline characteristics of groups receiving or not receiving these agents differed and residual confounding may have been present (18). The OPTIMAL-ACT trial will incorporate a pre-specified analysis with specific ACT targets in patients receiving GP IIb/IIIa inhibitors to better understand ACT targets and outcomes.

B.1.5 Aim 5 (Exploratory): We will explore the association of ACT targets with individual components of NACE and stent thrombosis for purposes of hypothesis generation.

C. Innovation/Experience: There are two innovative and unique aspects of this proposal. 1. This study will define the optimal ACT target during PCI. 2. Mayo Clinic ([name], senior author) has published the largest non-randomized (observational) study on the relation of ACT and outcomes in the peer-reviewed literature(18). Our observations that ACT values were associated with unadjusted events, but were not independently associated with outcome after multivariable adjustment, offers credible background evidence for performing a prospective trial (18) 2. This study will incorporate an evidence-based algorithm for UFH supplementation and ACT sampling frequency to provide critical standardization to the process of intra-procedural anticoagulation. In addition, the study will be novel in formally defining the use of the ACT target as the value prior to first coronary device activation, which is recommended as it is a single, unique value, and unbiased as compared to peak ACT or closing ACT values which are greatly influenced by sampling frequency. ACT prior to device activation has been used as the primary predictor variable in retrospective analyses from previous antiplatelet trials (19-21), however, the extant literature is not consistent with use of pre-device ACT values.

D. Approach: Patients >18 years of age referred for coronary angiography with intent to perform revascularization, if clinically indicated, will be prospectively identified and eligible for participation. . Patients who undergo adjunctive intracoronary imaging or physiologic assessment of lesion severity that requires administration of UFH and ACT sampling prior to coronary vessel wiring may also be randomized. The following inclusion criteria for OPTIMAL-ACT are as follows:

Inclusion Criteria:

- Age>18
- Ability of subject to give appropriate consent
- Referred for coronary angiography with **possible** coronary revascularization or adjunctive invasive diagnostic testing (IVUS/OCT, FFR, or iFR)

Specific exclusions would include patients receiving low-molecular weight heparin at treatment doses with last dose within 6 hours of coronary angiography (patients on low-molecular weight heparin (LMWH) for venous thromboembolism prophylaxis would be eligible), upstream treatment with GP IIb/IIIa inhibitors within the previous 72 hours, use of warfarin or a novel oral anticoagulant at the time of the procedure, patients being bridged with LMWH in the peri-procedural setting, PCI performed within the proceeding 30 days, need for rotational atherectomy, and planned use of bivalirudin as the procedural anticoagulant. If the operator was uncertain as to whether bivalirudin would be used, the patient would be eligible for screening and randomization. In the event that bivalirudin was selected to support the PCI procedure, the patient would be excluded from the OPTIMAL-ACT trial and recommendations would be for dosing bivalirudin per the manufacturer's instructions with ACT monitoring as used in the REPLACE-2 trial (22), which included ACT value 5 minutes after initial bolus and if <225 sec, an additional bolus of 0.3 mg/kg if needed. The following exclusion criteria for OPTIMAL-ACT are as follows:

[figure not shown]
Exclusion Criteria:

- Receipt of LMWH at treatment dose (not DVT prophylaxis dose) within 6 hours of coronary angiography
- Prior GP IIb/IIIa use within the previous 72 hours
- Use of warfarin (vitamin K antagonist) or direct oral anticoagulant
- Patients on LMWH bridging strategy
- PCI within prior 30 days
- Planned use of bivalirudin as the procedural anticoagulant
- Rotational atherectomy
- Excimer laser coronary angioplasty
- Chronic total occlusions
- Patients with active bleeding disorders or bleeding diathesis
- Patients with ST-segment elevation myocardial infarction
- Patient with clinical evidence of cardiogenic shock (defined as SBP<90 mmHg for ≥30 min OR support to maintain SBP ≥90 mmHg AND evidence of end-organ hypoperfusion (urine output <30 mL/h or cool extremities)
- Chronic kidney disease stage 4/5 (GFR 30 mL/min)

Patients would be randomized to one of three ACT target groups (Figure 1). Patients will undergo randomization (1:1:1) to either low ACT target, medium ACT target, or high ACT target using a software automatic program (insert information on SDMS). ACT target ranges would be modified based on intended or provisional use of GP IIb/IIIa inhibitors. Target ranges for the OPTIMAL-ACT trial were based on both review of practice guideline recommendations, including the uncertainty expressed in the guidelines regarding ACT values and outcomes (4), and consensus agreement by study interventional cardiologists regarding clinical equipoise in the target ranges studied. PCI would be performed per routine clinical practice and selection of adjunctive oral antiplatelet therapies would be at the discretion of the operator and in accordance with clinical practice guidelines (4). Patients would be observed post PCI for

[figure not shown]
bleeding (primary endpoint), defined as BARC 1, 2,3 or 5 and EASY I-V (Appendix) and for NACE (i.e., ischemic events or bleeding as the primary safety endpoint). Follow-up would extend for 30-days post PCI for occurrence of the primary endpoint and primary safety endpoint. A dedicated telephone script will be used to contact the patient 30 days post-procedure. If the patient experienced a possible endpoint event and was treated at an outside facility, medical records will be obtained for review of whether the endpoint was met.

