#### F. Statistical Considerations:

**F1. Randomization and blinding:** Patients will be randomized (1:1:1) to one of the three ACT target groups (low, medium, or high) using a dynamic minimization algorithm so as to optimize the likelihood that balance between the low, medium, and high ACT target groups will be

achieved with respect to sex (male or female) and glomerular filtration rate (30 to 59 ml/min/1.73m^2 or ≥60 ml/min/1.73m^2). The algorithm will be implemented in RAVE RTSM, a secure web-based interface, and accessed by the study coordinator or other appointed study personnel. Randomization will be conducted after the diagnostic portion of the procedure on only patients who will require ACT monitoring. Since eligible patients will require ACT monitoring during PCI, we will not conduct the study in a strictly blinded fashion. However, study participants will not be informed of their randomization assignment.

**F2. Data collection and handling:** Electronic case report forms along with a corresponding secure REDCap database will be created for data collection (29). Data to be collected will include baseline demographics, comorbidities, procedural variables, in-hospital events, NACE component, and adverse events.

**F3: Definition of study outcomes:** Study endpoints are summarized in Appendix II.

**F3.1 Primary study endpoint:** Our **primary study endpoint is bleeding** and is defined as either a Bleeding Academic Research Consortium (BARC) hemorrhage grade of 1, 2, 3, or 5 or an EASY hematoma scale grade of I-V from the time of PCI to the time the patient is discharged from the hospital.

**F3.2 Primary safety endpoint:** Our **primary safety endpoint is a composite of net adverse clinical events (NACE) and stent thrombosis**, as defined by the Academic Research Consortium, from the time of PCI to the time the patient is discharged from the hospital.

**F3.2.1 NACE** is the composite of all-cause mortality, myocardial infarction (MI), stroke, target lesion revascularization, and major bleeding within 30 days after PCI.

**F3.2.2 MI** will be defined as any two of the following 3 criteria: 1) chest pain for at least 20 minutes; 2) elevation of cardiac biomarkers, preferably troponin, above the laboratory upper limit of normal; and 3) new pathological Q wave on electrocardiogram.

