## F5. Statistical analysis plans:

F5.1 Patient population for analysis: The primary analysis will include all randomized patients. Since patients will be randomized after the diagnostic portion of the procedure and the primary study outcome will be collected during their initial hospitalization after PCI, we anticipate negligible loss to follow-up and negligible imbalance between study arms. Analysis of the study aims will be conducted using an intent-to-treat approach, which means it will be an analysis including all randomized patients according to the group they were randomized regardless of whether or not the assigned ACT target was achieved.

F5.2 Primary analysis plan: Aim 1: The risk of in-hospital bleeding in the medium ACT target group and the high ACT target group will be compared to the risk of in-hospital bleeding in the low ACT target group using pair-wise chi-square tests (or Fisher's exact test). Relative risks and 95% confidence intervals will be reported. For these two tests of the primary study outcome, a two-sided p-value  $\leq 0.025$  will be considered statistically significant using the Bonferroni adjustment for multiple testing. This means that the overall two-sided level of significance for the trial will be 0.05. Aim 2: We will estimate the proportion of patients with each outcome (bleeding, NACE) along with 95% confidence intervals for the proportions using the Wilson score method separately for the three groups. Aim 3: We will create a 95% confidence interval for the difference in proportions of patients with NACE in the low and high ACT target groups using the Newcombe score method. This will be used to assess whether there is evidence of non-inferiority of low ACT target compared to high ACT target according to the definition in section F3.4.

F5.3 Secondary analysis plan: We will evaluate if associations between ACT target group (low, medium, high) and in-hospital bleeding are independent of sex, access site, and concomitant use of glycoprotein (GP) IIb/IIIa inhibitors (Aim 2) using a Cochran-Mantel-Haenszel test. For these pre-planned tests, a two-sided p-value  $\leq 0.0167$  will be considered statistically significant using a Bonferroni adjustment for multiple testing. Descriptive summaries and relative risks will be reported as in the primary analysis, except stratified by each of the patient or procedure characteristics.

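### Patients may be randomized while bivalirudin use is undecided and are then excluded if it is chosen, but F5.1 analyzes everyone randomized

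*Combined protocol and SAP*

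**What the plan says.** Three parts of the plan bear on this.

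- **Section D, exclusions.** The narrative and the bulleted list both exclude "planned use of bivalirudin as the procedural anticoagulant", which can be judged before randomization. The narrative then adds: "If the operator was uncertain as to whether bivalirudin would be used, the patient would be eligible for screening and randomization". The next sentence reads: "In the event that bivalirudin was selected to support the PCI procedure, the patient would be excluded from the OPTIMAL-ACT trial". It goes on to mention ACT monitoring for patients given bivalirudin.
- **Section F1.** "Randomization will be conducted after the diagnostic portion of the procedure on only patients who will require ACT monitoring". On blinding: "we will not conduct the study in a strictly blinded fashion". Only participants are said to be kept unaware of their assignment.
- **Section F5.1.** "The primary analysis will include all randomized patients". Intent-to-treat is described as "including all randomized patients according to the group they were randomized regardless of whether or not the assigned ACT target was achieved". Bivalirudin is not mentioned.

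On a related eligibility point, Section D says that patients having imaging or physiology that "requires administration of UFH and ACT sampling prior to coronary vessel wiring may also be randomized". The endpoint windows in F3.1 and F3.2 nevertheless start at PCI.

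**The concern.** Read in order, Section D allows randomization during uncertainty and then removes the patient on a choice that may come later. It does not say whether excluded means off the ACT algorithm, out of follow-up, or out of the analysis. If the sentence is applied after randomization, randomized patients leave the trial and the groups compared are no longer the randomized ones.

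The operator may know the assigned target, so the choice of bivalirudin could depend on the arm. That is an inference; no section says it would happen. If higher-risk patients left the medium or high arm, a real bleeding difference would be understated. If they left the low arm, it would be exaggerated. The NACE non-inferiority comparison (Aim 3) is exposed in the same way. F5.1 would keep these patients, so staff following Section D and an analyst following F5.1 could end up with different data sets.

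**Working it through.** **1. The text, step by step**

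- Can a patient be randomized before the anticoagulant is settled? Yes: Section D says so for an undecided operator.
- Does F1 prevent it? No. Randomization follows the diagnostic portion, so the choice may already have been made, but nothing requires that. The need for ACT monitoring does not screen these patients out, because Section D describes ACT monitoring under bivalirudin too.
- What happens if bivalirudin is then chosen? Section D excludes the patient, with no time limit. F5.1 includes the patient.
- Does any section reconcile the two? No. Follow-up, analysis and replacement of such patients are not addressed. The 20% allowance in F.4 is for patients who never need ACT monitoring and so are never randomized.

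**2. The plan's own power figure**

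Inputs from F.4: 504 patients, so 504/3 = 168 per arm; bleeding 5% (low), 15% (medium), 25% (high); two-sided 0.025 per test; more than 80% power.

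Exact binomial enumeration of the uncorrected chi-square test gives 81.2% for low versus medium and 81.1% for both comparisons together. The stated power reproduces. The pooled-variance normal approximation gives 79.5% for low versus medium.

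**3. Removal from one arm (illustration)**

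The documents give no bivalirudin rate, timing or relative risk, so these are assumed. Let s be the share of one arm removed and k the bleeding risk of those removed relative to the arm average p. The rate in those who remain is p(1 − s·k)/(1 − s). Shares of 2%, 5% and 10% of 168 are 3, 8 and 17 patients.

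Example, medium arm, s = 5%, k = 2: 0.15 × (1 − 0.10)/0.95 = 0.1421. The expected difference is 0.1421 − 0.05 = 0.0921, or 9.2 points instead of 10.0. Low-versus-medium power falls to 74.5%.

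The same loss from the low arm, with a true rate of 15% in both arms, creates a difference of 0.15 − 0.1421 = 0.0079, or 0.8 points. The per-test false-positive rate is 2.7% against 2.5%.

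| Assumed loss, one arm only | Expected difference (points) | Low-vs-medium power | Spurious difference under no effect (points) | False-positive rate per test |
|---|---|---|---|---|
| 2%, k = 1 to 3 | 10.0 to 9.4 | 81% to 77% | 0 to 0.6 | 2.5% to 2.7% |
| 5%, k = 2 | 9.2 | 74.5% | 0.8 | 2.7% |
| 2% to 10%, k = 1 to 3 | 10.0 to 6.7 | 81% to 47% | 0 to 3.3 | 2.4% to 8.2% |

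The worst corner is 0.15 × (1 − 0.30)/0.90 = 0.1167, a difference of 6.7 points. It needs 10% of one arm removed at three times average risk and none from the other. If the loss falls on the high arm instead, low-versus-high power stays at about 97% or above across the grid.

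**4. Equal random removal, and retention**

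Equal random removal does not bias the contrast. Power for both tests is 80.3% at 2% loss (165 per arm) and 78.8% at 5% (160 per arm).

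For retention, suppose switched patients bleed at a common rate q of 5% to 15% whatever their arm. Each arm's rate becomes (1 − s)p + s·q, and power for both tests is:

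| Share retained | Power, q = 5% to 15% |
|---|---|
| 2% | 79.7% to 78.8% |
| 5% | 77.4% to 75.1% |
| 10% | 73.2% to 68.5% |

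Small distances from 80% should not be read as evidence. The normal approximation is already below it with no loss, and 5000 simulations carry a standard error of √(0.811 × 0.189/5000) = 0.0055, about 0.55 points.

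**The case against.** The strongest reply is that the bivalirudin sentences belong to an eligibility paragraph. Consent comes before the procedure and randomization after the diagnostic portion. The text can therefore be read as: indecision does not bar enrolment, and a patient for whom bivalirudin is then chosen fails eligibility. On that reading most exclusions precede randomization. F5.1 is also the only place that defines the analysis population, so an analyst has one rule. Finally, the one-arm scenarios rest on assumptions stacked together, and keeping switched patients costs power rather than gaining it.

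Much of this stands. The reading may well limit how often the conflict arises, dependence on arm is only a possibility, effects at 2% loss are small, and retention at 5% gives less power (77.4% to 75.1%) than equal random removal (78.8%). None of it resolves the conflict. Section D expressly extends eligibility to randomization during uncertainty and sets no time limit on the exclusion. F5.1 cannot be carried out for patients whose follow-up ended because site staff took them to be out of the trial.

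**Conclusion.** The concern holds and should be fixed. As written, Section D permits an exclusion after randomization in a trial that is not strictly blinded, and F5.1 contradicts it. That conclusion rests on the text alone and needs no assumed rate.

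The effect on results cannot be sized from the documents: frequency, magnitude and direction all depend on how many patients switch, when, in which arm and at what risk. Under the assumptions shown, it runs from negligible to material. The sample size calculation itself is not in error. Confidence is medium, because the choice of anticoagulant may usually precede randomization in practice.

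A separate, secondary point also stands. Section D and F.4 allow imaging or physiology patients to be randomized, while F.4 also makes receipt of PCI the last eligibility condition. A patient randomized without PCI would be in the F5.1 population with no stated start to the in-hospital windows. No share of such patients is claimed, and the main conclusion does not depend on this.

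**What to change.** Reconcile Section D with F5.1 in both places:

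- State that the bivalirudin exclusion applies only before randomization.
- State that every randomized patient is followed and analyzed in the assigned arm, whatever anticoagulant is used later.
- Report the number switched to bivalirudin by arm.
- Optionally, record the intended anticoagulant before randomization. This would narrow the undecided enrolment that Section D now allows.

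Separately, align the eligibility wording across B.1.1, D, F1, F.4 and F5.1, and start the endpoint windows at randomization or the index procedure, so that every analyzed patient has a defined window.

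The cost is a few sentences and one count by arm, plus the dilution from retained patients shown above. The gain is protection against bias and a single analysis set, not power. Nothing here bears on which anticoagulant should be used.
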